Study drug administration will begin on Day 1 (Visit 2) following randomization. All patients will receive standard of care and/or EUA treatment for COVID-19 in addition to the study drug. Patients will continue study drug treatment BID through Day 27 and take 1 dose on Day 28. If a patient is discharged from the hospital prior to Day 28, he/she will continue treatment as an outpatient at home with his/her assigned treatment (FP-025 100 mg BID, FP-025 300 mg BID, or placebo BID) until Day 28. Dosing instructions will be provided prior to discharge. Although treatment will be identical for inpatients and outpatients, patients discharged from the hospital will follow a different Schedule of Procedures, characterized by telemedicine (or telephone, if sites and/or patients do not have video capability) visits. The End of Treatment (EOT) Visit on Day 28 will be identical for all patients (with the exception of the arterial oxygen partial pressure [PaO₂]/fractional inspired oxygen [FiO₂] ratio, performed only in patients on invasive or non-invasive ventilation) and will include a high-resolution, non-contrast CT scan, in addition to other assessments.

After treatment is completed, all patients will undergo 2 follow-up assessments during the Follow-Up Period. The first follow-up will be a telephone visit on Day 45 to assess concomitant medications, adverse events (AEs), and the NIAID 8-point ordinal scale for COVID-19 and hospitalization outcomes score. The second follow-up will be an in-person visit on Day 60 and

will include a high-resolution, non-contrast CT scan and pulmonary function tests, in addition to other assessments.

An iDMC will convene to oversee safety and efficacy assessments during and after the Phase 2 study. The first iDMC meeting will occur after approximately 10 to 15 patients have been enrolled. The second iDMC meeting will occur after approximately 50% to 60% of patients have been enrolled. No formal statistical testing will be conducted. In addition, when all patients in the Phase 2 study have completed the EOT Visit on Day 28, a primary analysis will be conducted by an independent statistician and reviewed by the iDMC.

Phase 3:

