7.1.1 Primary Efficacy Endpoint

The primary efficacy endpoint is the proportion of patients alive and not requiring non-invasive or invasive ventilation (ie, not receiving high-flow nasal cannula, non-invasive positive pressure ventilation, invasive mechanical ventilation, or ECMO) at Day 28, with each dose (Phase 2) or the optimal dose (Phase 3) of FP-025 compared to placebo.

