7.1.2 Key Secondary Efficacy Endpoints

The key secondary efficacy endpoints include the following, with each dose (Phase 2) or the optimal dose (Phase 3) of FP-025 compared to placebo:

- Proportion of patients on invasive mechanical ventilation at Day 28;
- Proportion of patients alive at Day 28;
- Proportion of patients alive and not requiring non-invasive or invasive ventilation (ie, not receiving high-flow nasal cannula, non-invasive positive pressure ventilation, invasive mechanical ventilation, or ECMO) at Day 60;
- Proportion of patients on invasive mechanical ventilation at Day 60; and
- Proportion of patients alive at Day 60.

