7.1.3 Other Secondary Efficacy Endpoints

The other secondary efficacy endpoints include the following, with each dose (Phase 2) or the optimal dose (Phase 3) of FP-025 compared to placebo:

- Quantitative assessment of lung fibrosis at Day 28 and at Day 60 using high-resolution, non-contrast CT scan;
- Proportion of patients who were randomized on invasive mechanical ventilation who are free of invasive mechanical ventilation at Day 28 and at Day 60;
- Number of ventilator-free days (ie, days free of invasive mechanical ventilation) at Day 28 and at Day 60;
- Number of ICU-free days at Day 28 and at Day 60;
- Number of days in the hospital at Day 28 and at Day 60;
- Change from baseline in peripheral capillary oxygen saturation (SpO₂) at Day 28 and at Day 60;
- Change from baseline in PaO₂/FiO₂ ratio at Day 28 and at Day 60 (patients on invasive or non-invasive ventilation only);
- Proportion of patients alive and not hospitalized at Day 28 and at Day 60;

- Proportion of patients with disease progression (defined as a ≥ 2 -point decrease in the NIAID 8-point ordinal scale score or death) at Day 28 and at Day 60;
- Proportion of patients who improve by ≥ 2 points on the NIAID 8-point ordinal scale scores at Day 28 and proportion of patients who improve by ≥ 2 points at Day 60;
- Pulmonary function at Day 28 (if possible based on the patient's clinical condition per the judgment of the Investigator) and at Day 60 (all patients) based on the following scores:
 - Forced vital capacity (FVC);
 - Forced expiratory volume in 1 second (FEV₁);
 - FEV₁/FVC ratios; and
 - Diffusing capacity of the lungs for carbon monoxide; and
- Change from baseline in eGFR, blood urea nitrogen, and serum creatinine at Day 28 and Day 60.

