7.2 Efficacy Assessments

7.2.1 Arterial Oxygen Partial Pressure/Fractional Inspired Oxygen Ratio

A PaO_2 , obtained via arterial blood gas will be used to calculate the $\text{PaO}_2/\text{FiO}_2$ ratio, only in patients on invasive or non-invasive ventilation.

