AE = adverse event; BAL = bronchoalveolar lavage; BID = twice daily; C4M = neo-epitope of MMP-2, 9-, and 12-mediated degradation of type IV collagen; C6M = neo-epitope of MMP-2-mediated degradation of type VI collagen; CoV = coronavirus; CRPM = neo-epitope of MMP-1 and 8-mediated degradation of C-reactive protein; CT = computed tomography; ECG = electrocardiogram; eCRF = electronic case report form; EOT = End of Treatment; ET = Early Termination; FEV₁ = forced expiratory volume in 1 second; FiO₂ = fractional inspired oxygen; FVC = forced vital capacity; hCG = human chorionic gonadotropin; I/E = inclusion and exclusion; ICF = informed consent form; IFN = interferon; IL = interleukin; MMP = matrix metalloproteinase; NIAID = National Institute of Allergy and Infectious Diseases; PaO₂ = arterial oxygen partial pressure; PCR = polymerase chain reaction; PFT = pulmonary function test; PK = pharmacokinetic(s); PRO-C3 = released N-terminal pro-peptide of type III collagen; PRO-C4 = internal epitope in the 7S domain of type IV collagen; PRO-C6 = C-terminal of released C5 domain of type VI collagen α 3 chain (endotrophin); reC1M = neo-epitope of MMP-2, 9-, and 13-mediated degradation of type I collagen; SARS = severe acute respiratory syndrome; SpO₂ = peripheral capillary oxygen saturation; TGF = transforming growth factor; TNF = tumor necrosis factor; WCBP = woman/women of childbearing potential; X-FIB (D-dimer) = neo-epitope of plasmin-mediated degradation of cross-linked fibrin.

Table 3. Modified Schedule of Procedures for Discharged Patients

Visit	Treatment Period					Follow-Up Period		ET Visit ^f
	Day of Discharge ^a	O1 ^b	O2 ^b	O3 ^b	11/EOT	12	13	
Study Day	X ^c	X + 7 ^d	X + 14 ^d	X + 21 ^d	28	45 ^e	60	
Visit Window (Days)	±2	±3	±3	±3	±3	±7	±7	Unscheduled
Assessment of standard of care treatment ^g	X-----				X			
Prior/concomitant medications	X-----				X	X	X	
Weight	X				X		X	X
Physical examination ^h	X	X	X	X	X		X	X
Vital signs including SpO ₂ ⁱ	X	X	X	X	X		X	X
Urine hCG ^j					X		X	X
12-lead ECG ^k	X				X			X
Clinical laboratory assessments ^l	X				X		X	X
PK blood sampling ^m					X			
Study drug provided for rest of study period	X							
Study drug self-administration ⁿ		X	X	X	X			
High resolution, non-contrast CT scan of the chest					X		X	X
PFTs ^o							X	X
Biomarker assessment (blood) ^p	X				X		X	X
NIAID 8-point ordinal scale assessment	X				X	X	X	X
AEs/SAEs ^q	X	X-----					X	X

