C4M = neo-epitope of MMP-2, 9, and 12-mediated degradation of type IV collagen; C6M = neo-epitope of MMP-2-mediated degradation of type VI collagen; CRPM = neo-epitope of MMP-1 and 8-mediated degradation of C-reactive protein; IL = interleukin; MMP = matrix metalloproteinase; PRO-C3 = released N-terminal pro-peptide of type III collagen; PRO-C4 = internal epitope in the 7S domain of type IV collagen; PRO-C6 = C-terminal of released C5 domain of type VI collagen α3 chain (endotrophin); reC1M = neo-epitope of MMP-2, 9, and 13-mediated degradation of type I collagen; X-FIB (D-dimer) = neo-epitope of plasmin-mediated degradation of cross-linked fibrin.

APPENDIX C: NATIONAL INSTITUTE OF ALLERGY AND INFECTIOUS DISEASES 8-POINT ORDINAL SCALE FOR COVID-19 AND HOSPITALIZATION OUTCOMES

Table 4. NIAID 8-Point Ordinal Scale for COVID-19 and Hospitalization Outcomes

Numerical Score	Definition
1	Death
2	Hospitalized, on invasive mechanical ventilation or extracorporeal membrane oxygenation
3	Hospitalized, on non-invasive ventilation or high-flow oxygen devices
4	Hospitalized, requiring supplemental oxygen
5	Hospitalized, not requiring supplemental oxygen – requiring ongoing medical care (COVID-19-related or otherwise)
6	Hospitalized, not requiring supplemental oxygen – no longer requires ongoing medical care
7	Not hospitalized, limitation on activities and/or requiring home oxygen
8	Not hospitalized, no limitation on activities

COVID-19 = coronavirus disease 2019; NIAID = National Institute of Allergy and Infectious Diseases.
Source: Adaptive COVID-19 treatment trial (ACTT). NIH clinicaltrials.gov website.
<https://clinicaltrials.gov/ct2/show/NCT04280705>. Accessed 09 November 2020

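### Change in PaO2/FiO2 at Day 28 and Day 60 is listed as a comparison with placebo but exists only in patients still on support at the visit; it should be a descriptive summary

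*Combined protocol and SAP*

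**What the plan says.** Section 7.1.3 and the synopsis introduce the other secondary endpoints as assessed "with each dose (Phase 2) or the optimal dose (Phase 3) of FP-025 compared to placebo". One of them is change from baseline in the PaO2/FiO2 "ratio at Day 28 and at Day 60 (patients on invasive or non-invasive ventilation only".

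Several places tie the restriction to ventilation status at the visit:

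- The synopsis and Section 3.1.1 make the ratio the one exception to an otherwise identical Day 28 visit: "performed only in patients on invasive or non-invasive ventilation".
- Section 7.2.1 and Appendix A, Table 2, footnote i have the ratio calculated "only in patients on invasive or non-invasive ventilation".
- The outpatient schedule, "Table 3. Modified Schedule of Procedures for Discharged Patients", has no PaO2/FiO2 row.

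A primary responder (Section 7.1.1) is alive and "not receiving high-flow nasal cannula, non-invasive positive pressure ventilation, invasive mechanical ventilation, or ECMO" at Day 28. The same status at Day 60 is a key secondary endpoint (Section 7.1.2).

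The method for other secondary endpoints is left to the SAP (Section 9.2.1.2), as are data handling and imputation (Section 9.2.1). The supplied text contains no SAP detail on this endpoint.

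**The concern.** A patient has a Day 28 or Day 60 ratio only if still alive and still on support, which is essentially failure on the outcome that the drug is meant to improve. If the drug frees patients from support or prevents deaths, it changes who is left in the measured group, and it does so in one arm only. A difference in mean change then mixes any effect on oxygenation with a difference in case mix. Randomization balances the arms at entry, not within a group formed by outcome.

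At stake is one secondary estimate that could mislead. Phase 2 has no alpha control, and at the Phase 3 futility look the iDMC is to weigh all available efficacy data (Section 9.2.3), so the figure could be read even though nothing formal depends on it.

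**Working it through.** **1. The plan's own figure.** Section 9.2.5 gives 304 patients (152 per arm) for 60% vs 75%, 1-sided 0.025 and about 80% power. With a pooled variance under the null, n per arm = [1.960 × √(2 × 0.675 × 0.325) + 0.842 × √(0.60 × 0.40 + 0.75 × 0.25)]² / 0.15² = 151.9, rounded up to 152. The figure reproduces, and power at 152 per arm is 0.800. No sample size or power is stated for PaO2/FiO2.

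**2. Expected size of the measured group at Day 28, before deaths are removed.** This is n × (1 − response rate).

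- Phase 3: placebo 152 × 0.40 = 60.8; drug 152 × 0.25 = 38.0.
- Phase 2, if the same rates held with 33 per arm: 33 × 0.40 = 13.2; 33 × 0.25 = 8.25.

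The documents give no Day 60 rates and no trial death rate.

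**3. After deaths (assumed).** Control mortality is taken as 15% or 25%. The shift that moves response from 60% to 75% on a normal scale is 0.674 − 0.253 = 0.421 SD. Applied to the death threshold as well, it gives drug mortality of 7.3% or 13.7%.

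- 15% case: 152 × (0.40 − 0.15) = 38 vs 152 × (0.25 − 0.073) ≈ 27.
- 25% case: 152 × (0.40 − 0.25) ≈ 23 vs 152 × (0.25 − 0.137) ≈ 17.

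**4. Sampling error.** The 95% CI half-width is 1.96 × SD × √(1/n1 + 1/n2), with an assumed SD of 60 to 80 mmHg.

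- 38 vs 27: 29.6 to 39.5 mmHg.
- 23 vs 17: 37.6 to 50.2 mmHg.

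**5. Direction and size of the bias (simulation, every parameter assumed).** Day 28 severity correlates 0.3 to 0.7 with baseline severity. A score that decides off support, on support or dead correlates k = 0.3 to 1.0 with Day 28 severity. Baseline ratio = 150 − 45 × baseline severity + noise (SD 30). Day 28 ratio = 250 − 60 × Day 28 severity + noise (SD 40). The drug moves the proportion alive and off support from 60% to 75% in one of two ways:

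- *Through oxygenation.* Day 28 severity falls by 0.421/k, so the true effect is 60 × 0.421/k, or 25 mmHg at k = 1 and 84 mmHg at k = 0.3. The true 25 mmHg appears as about 6 to 14 mmHg. Over the whole range, 25 to 84 mmHg appears as about 6 to 81 mmHg. The effect is attenuated and never reversed.
- *Without oxygenation change.* Only the support/death score shifts, so the true effect is zero. The measured group shows drug worse by about 3 to 20 mmHg.

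In both cases the bias is usually smaller than the half-width in step 4.

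**6. High-flow nasal cannula.** Section 7.1.1 spells out ventilation as a list that includes high-flow nasal cannula. The ordinal scale (Appendix C, Table 4) has a category "Hospitalized, on non-invasive ventilation or high-flow oxygen devices", which names the two separately. High-flow is also a route of entry (Section 4.1). If it does not count for the blood gas, the measured group is smaller than in step 2.

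**The case against.** The strongest case against is that no faulty analysis is on the page. Comparison with placebo is a stem shared by every efficacy list, including the exploratory biomarkers, and it announces no test. The SAP may already treat this endpoint descriptively. The restriction is stated openly, the outcomes that would reveal selection are endpoints themselves, and the endpoint carries no alpha. This limits the reach of the point but does not remove it: as the protocol defines the endpoint, the comparison is conditioned on outcome, and nothing in the supplied text repairs that.

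Three stronger readings are tempting, and the documents do not support them:

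- *A reader might infer that an effective drug will look harmful on this endpoint.* The wrong sign arises in the model only if patients come off support with no change in oxygenation. If the benefit acts through oxygenation, the result is attenuation. The documents do not say which applies.
- *A reader might take 61 and 38 as ceilings.* They are expected counts at the design rates. The Day 28 visit also has a window of ±3 days (±7 at Day 60), while event endpoints are timed in days from randomization. A patient with a blood gas on support at Day 25 can therefore still be a Day 28 responder.
- *A reader might see a threat to the trial's main conclusion.* The endpoint is not in the fixed sequence of Section 9.2.1.3.

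The high-flow question is also modest, since the primary endpoint's wording favours inclusion. One sentence would settle it.

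**Conclusion.** The point holds with limited reach. That the measured group is defined after randomization, and is essentially the living non-responders, follows from the protocol text and needs no assumption. The counts of about 61 vs 38 rest on the design response rates. The mmHg figures are illustrations on assumed mortality, SDs and correlations; they show that the bias depends on mechanism, not how large it will be in this trial. The measured group is small enough that imprecision would usually outweigh the bias, which is a further reason to draw no inference from it. Type I error for the hierarchy, the primary analysis and N = 304 are unaffected. It is a low-priority change worth making because it costs little.

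**What to change.** In the SAP, and in the synopsis and Section 7.1.3 at the next protocol amendment:

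- Present the on-support PaO2/FiO2 change at Day 28 and Day 60 as a descriptive summary by arm, with no between-arm test and no efficacy conclusion.
- Beside it, report per arm the numbers measured, on support but not measured, off support, dead, and of unknown status.
- State whether patients on high-flow nasal cannula are included.

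This is a wording change that uses data already collected. A SAP sentence is enough for now, so no amendment is needed for this alone. The cost is that the mmHg comparison is lost as an efficacy endpoint.

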7.1.4 Exploratory Endpoints

Exploratory endpoints will include the change from baseline (pre-dose on Day 1) in biomarkers related to pulmonary inflammation, fibrosis and/or lung injury at Day 7, Day 14, Day 28, and Day 60, including but not limited to the following, with each dose (Phase 2) or the optimal dose (Phase 3) of FP-025 compared to placebo:

- MMP-12, MMP-7, and MMP-9;
- Transforming growth factor- β ;
- Connective tissue growth factor;
- C-reactive protein (CRP);
- Cytokines (IFN- γ , tumor necrosis factor [TNF]- α , IL-6, IL-1 β , and C-C motif chemokine ligand 2 [monocyte chemoattractant protein-1]);
- Ferritin;
- Released N-terminal pro-peptide of type III collagen;
- Internal epitope in the 7S domain of type IV collagen;
- C-terminal of released C5 domain of type VI collagen $\alpha 3$ chain (endotrophin);
- Neo-epitope of MMP-2, 9, and 13-mediated degradation of type I collagen;
- Neo-epitope of MMP-2, 9, and 12-mediated degradation of type IV collagen;
- Neo-epitope of MMP-2-mediated degradation of type VI collagen;
- Neo-epitope of MMP-1 and 8-mediated degradation of CRP; and
- Neo-epitope of plasmin-mediated degradation of cross-linked fibrin.

Additional biomarkers not listed here may be evaluated at a future date.

7.1.5 Pharmacokinetic Endpoint

The PK endpoint is the plasma exposure of FP-025 at each dose level. Sampling times will be as follows:

- Day 1 (Visit 2): pre-dose, 1 hour (± 10 minutes), 3 hours (± 10 minutes), and 8 hours (± 10 minutes) post the first morning dose of study drug;

Note: If the patient is randomized in the afternoon on Day 1 (Visit 2), this will be performed after the morning dose of study drug on Day 2.

- Day 4, Day 7, Day 14, and Day 21: within 1 hour (± 10 minutes) prior to the morning dose; and
- Day 28: within 1 hour (± 10 minutes) prior to the morning dose and 1 hour (± 10 minutes) post-morning dose.

7.2 Efficacy Assessments

7.2.1 Arterial Oxygen Partial Pressure/Fractional Inspired Oxygen Ratio

A PaO_2 , obtained via arterial blood gas will be used to calculate the $\text{PaO}_2/\text{FiO}_2$ ratio, only in patients on invasive or non-invasive ventilation.

7.2.2 Pulmonary Function Tests

Pulmonary function tests (PFTs) will be performed at the times indicated in Appendix A. PFTs will include measurement of FVC, FEV_1 , FEV_1/FVC ratio, and diffusing capacity of the lungs for carbon monoxide.

7.2.3 Computed Tomography Scan

A high-resolution, non-contrast CT scan will be performed at the times indicated in Appendix A to assess for lung fibrosis. The CT scan will be acquired with a single acquisition of reduced dose (ie, 6 mSv total). A chest radiograph may be substituted for the high-resolution, non-contrast CT scan at the Screening Visit only for study eligibility.

7.2.4 Inflammatory and Fibrotic Biomarker Analysis

Biomarker analyses will be performed at the times indicated in Appendix A. Biomarkers include, but are not limited to, assessments of MMP-12, MMP-7, MMP-9, TGF- β , connective tissue growth factor, CRP, cytokines (IFN- γ , TNF- α , IL-6, IL-1 β , and C-C motif chemokine ligand 2 [monocyte chemoattractant protein-1]), ferritin levels, released N-terminal pro-peptide of type III collagen, internal epitope in the 7S domain of type IV collagen, C-terminal of released C5 domain of type VI collagen α 3 chain (endotrophin), neo-epitope of MMP-2, 9, and 13-mediated degradation of type I collagen, neo-epitope of MMP-2, 9, and 12-mediated degradation of type IV collagen, neo-epitope of MMP-2-mediated degradation of type VI collagen, neo-epitope of MMP-1 and 8-mediated degradation of CRP, and neo-epitope of plasmin-mediated degradation of cross-linked fibrin in blood.

Blood will be collected from patients that have consented (or whose LAR has consented) to the procedure. The blood samples will be collected per the laboratory manual instructions and analyzed. Samples may be stored at the central laboratory for future analyses.

7.2.5 National Institute of Allergy and Infectious Diseases 8-Point Ordinal Scale

The NIAID 8-point ordinal scale score will be assessed at the times indicated in Appendix A. The NIAID 8-point ordinal scale is described in detail in Appendix C.

7.3 Other Assessments

7.3.1 Severe Acute Respiratory Syndrome Coronavirus-2 Testing

SARS-CoV-2 testing may be performed at the Screening Visit. The patient must have a documented, laboratory-confirmed SARS-CoV-2 infection as determined by reverse transcriptase polymerase chain reaction (or an equivalent test) immediately prior to or during the current hospitalization to be included in the study.

8 SAFETY ASSESSMENTS

8.1 Adverse Events

An AE is defined as any untoward medical occurrence in a clinical investigation patient administered a pharmaceutical product, which does not necessarily have a causal relationship with this treatment. An AE can therefore be any unfavorable and/or unintended sign (including an abnormal laboratory finding), symptom, or disease temporally associated with the use of an investigational medicinal product, whether or not related to the investigational medicinal product. All AEs, including observed or volunteered problems, complaints, or symptoms, are to be recorded on the appropriate eCRF.

AEs will be monitored and recorded from the time of the first dose of study drug (Day 1 [Visit 2]) until the end of the study (Day 60). All events occurring prior to the first dose of study drug will be recorded as medical history. Patients should be instructed to report any AE that they experience to the Investigator, whether or not they think the event is due to study treatment. Beginning at Day 1 (Visit 2), Investigators should make an assessment for AEs at each visit and record the event on the appropriate AE eCRF.

Wherever possible, a specific disease or syndrome rather than individual associated signs and symptoms should be identified by the Investigator and recorded on the eCRF. However, if an observed or reported sign or symptom is not considered a component of a specific disease or syndrome by the Investigator, it should be recorded as a separate AE on the eCRF. Additionally, the condition that led to a medical or surgical procedure (eg, surgery, endoscopy, tooth extraction, or transfusion) should be recorded as an AE, not the procedure itself.

Any medical condition already present prior to the first dose of study drug should be recorded as medical history and not be reported as an AE unless the medical condition or signs or symptoms present at baseline changes in severity, frequency, or seriousness at any time during the study. In this case, it should be reported as an AE.

Clinically significant abnormal laboratory or other examination (eg, electrocardiogram [ECG]) findings that are detected during the study or are present at the Day 1 (Visit 2) and significantly worsen during the study should be reported as AEs, as described below. The Investigator will exercise his or her medical and scientific judgment in deciding whether an abnormal laboratory finding or other abnormal assessment is clinically significant. Clinically significant abnormal laboratory values occurring during the study will be followed until repeat tests return to normal, stabilize, or are no longer clinically significant. Abnormal test results that are determined to be an error should not be reported as an AE. Laboratory abnormalities or other abnormal clinical findings (eg, ECG abnormalities) should be reported as an AE if any of the following are applicable:

- If an intervention is required as a result of the abnormality;
- If action taken with the study drug is required as a result of the abnormality; or
- Based on the clinical judgment of the Investigator.

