8.1.4 Expected Acute Respiratory Distress Syndrome Events

As events of progression of the patient's underlying COVID-19 diagnosis will be captured as efficacy endpoints (see Section 7.1), these events should not be reported as AEs or SAEs unless considered related to the study drug or a study procedure or if the outcome is fatal during the study and within the safety reporting period. Additionally, expected events for ARDS that are perceived by the Investigator to occur with reasonable frequency in the day-to-day care of patients with ARDS treated in an ICU setting with mechanical ventilation will not be reported as AEs. Examples of events that are expected in the course of ARDS include transient hypoxemia, agitation, delirium, etc. Such events, which are often the focus of prevention efforts as part of standard ICU care, will not be considered reportable AEs unless the event is considered by the Investigator to be associated with the study drug or study procedures, is unexpectedly severe or frequent, or is a change of severity for an individual patient with ARDS.

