8.3 Serious Adverse Event Reporting – Procedures for Investigators

Initial reports

All SAEs occurring from the time of the first dose of study drug until Day 60 (approximately 30 days following the last dose of study drug) must be reported to Medpace Clinical Safety within 24 hours of the knowledge of the occurrence. After the 30-day reporting window, any SAE that the Investigator considers related to study procedures must be reported to the Medpace Clinical Safety or the Sponsor/designee.

To report the SAE, complete the SAE form electronically in the electronic data capture (EDC) system for the study. When the form is completed, Medpace Safety personnel will be notified electronically by the EDC system and will retrieve the form. If the event meets serious criteria and it is not possible to access the EDC system, send an email to Medpace Safety at [contact] or call the Medpace SAE reporting line (telephone number listed below), and fax/email the completed paper SAE form to Medpace (contact information listed in Section 8.6) within 24 hours of awareness. When the EDC system becomes available, the SAE information must be entered within 24 hours of the system becoming available.

Follow-up reports

The Investigator must continue to follow the patient until the SAE has subsided or until the condition(s) becomes chronic in nature, stabilizes (in the case of persistent impairment), or the patient dies.

Within 24 hours of receipt of follow-up information, the Investigator must update the SAE form electronically in the EDC system for the study and submit any supporting documentation (eg, patient discharge summary or autopsy reports) to Medpace Clinical Safety via fax or email. If it is not possible to access the EDC system, refer to the procedures outlined above for initial reporting of SAEs.

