APPENDIX A: SCHEDULE OF PROCEDURES

Table 2. Schedule of Procedures: Inpatient Admission Through Day 28

	Screening Visit	Treatment Period							Follow-Up Period		ET Visit ^b
		1	2	3	4	5	6	7/EOT	8	9	
Visit	-1 to 1	1	4	7	14	21	28	45 ^a	60		
Study Day											
Visit Window (Days)	-	±3	±3	±3	±3	±3	±3	±3	±7	±7	Unscheduled
Informed consent ^c	X										
I/E criteria	X	X ^d									
Demographic information	X										
Medical/surgical history	X	X ^d									
Assessment of standard of care ^e		X-----X									
Prior/concomitant medications	X	X-----X							X	X	X
Weight and height ^f	X	X						X		X	X
Physical examination ^g	X	X	X	X	X	X	X			X	X
Vital signs including SpO ₂ ^h	X	X	X	X	X	X	X			X	X
PaO ₂ /FiO ₂ ratio ⁱ	X	X	X	X	X	X	X			X	X
hCG ^j	X						X			X	X
Viral respiratory panel ^k	X										
12-lead ECG ^l		X	X	X	X	X	X				X
SARS-CoV-2 PCR ^m	X										
Clinical laboratory assessments ⁿ	X	X	X	X	X	X	X		X		X
PK blood sampling ^o		X	X	X	X	X	X				
Randomization		X									

Footnotes at the end of table.

Table 2. Schedule of Procedures: Inpatient Admission Through Day 28 (Continued)

	Screening Visit	Treatment Period							Follow-Up Period		ET Visit ^b
		1	2	3	4	5	6	7/EOT	8	9	
Visit	-1 to 1	1	4	7	14	21	28	45 ^a	60		
Study Day											
Visit Window (Days)	–	±3	±3	±3	±3	±3	±3	±7	±7	Unscheduled	
Study drug administration ^b		X	X	X	X	X	X				
High resolution, non-contrast CT scan of the chest ^a	X						X		X	X	
PFTs ^c									X	X	
Biomarker assessment (blood) ^d		X		X	X		X		X	X	
NIAID 8-point ordinal scale assessment		X	X	X	X	X	X	X	X	X	
AEs/SAEs ^e	X							X		X	

Note: If the study drug is discontinued but the patient is remaining in the study, the patient should be encouraged to remain in the study and to follow-up for key study visits (Day 28 and Day 60) but will not be required to attend every study visit. If the patient withdraws, he/she should complete the ET Visit.

- a. The Day 45 visit will be a telephone visit only.
- b. If a patient withdraws prematurely from the study, study staff should make every effort to complete the full panel of assessments scheduled for the ET visit. The reason for patient withdrawal must be documented in the eCRF.
- c. The Investigator will obtain written informed consent from each patient before any study-specific activity is performed.
- d. I/E criteria and medical/surgical history will be reviewed again on Day 1 (Visit 2) prior to randomization. Any updates since the Screening Visit will be assessed.

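### An SAE caused by a study procedure between consent and first dose has no required 24-hour report, although such an SAE is reportable after the window closes

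*Combined protocol and SAP*

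**What the plan says.** The start of collection is the same wherever the protocol sets it. Section 8.1 begins AE recording at the first dose on Day 1 (Visit 2) and continues: "All events occurring prior to the first dose of study drug will be recorded as medical history". The synopsis (Safety Endpoints) has the same rule. Footnote t to Table 2 and footnote q to Table 3 in Appendix A repeat the first-dose start. Section 8.3 sets the 24-hour SAE obligation for "All SAEs occurring from the time of the first dose of study drug until Day 60".

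Section 8.1 has one route from medical history into the AE data. A condition present before the first dose is not an AE "unless the medical condition or signs or symptoms present at baseline changes in severity, frequency, or seriousness at any time during the study".

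Study procedures appear in the safety rules in two ways. Section 8.3 says: "After the 30-day reporting window, any SAE that the Investigator considers related to study procedures must be reported". Sections 8.1.4 and 8.2 exempt COVID-19 progression events from reporting "unless considered related to the study drug or a study procedure", or unless the outcome is fatal within the safety reporting period.

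Section 9.1 defines the ITT Population as all randomized patients and limits the Safety Population to those who received at least one dose.

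**The concern.** Section 11.3 requires consent before any study-specific activity, so study procedures are done on consented patients before the first dose. If one of them causes a serious event, the rule sends it to medical history, the place for conditions the patient brought to the trial. Harm caused by the trial is then filed as background, and nothing in Section 8.3 requires it to be sent to the safety group within 24 hours.

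Section 8.3 is also asymmetric. A procedure-related SAE must be reported after the window closes, but no matching sentence covers the time before it opens. The protocol gives no reason for the difference.

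A second, smaller matter concerns patients who are randomized but not yet dosed. A death or SAE at that point follows allocation, yet it lies outside the SAE window, and a patient who is never dosed lies outside the Safety Population. At stake are complete reporting of procedure harm in critically ill patients and a full account of what happened to everyone randomized. No efficacy estimate depends on it.

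**Working it through.** The protocol gives no figure to reproduce, so the check sets the texts side by side.

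**1. Where does collection start?** Synopsis, Section 8.1, Section 8.3, footnote t and footnote q: all five use the first dose. None makes an exception for serious or procedure-related events. In the text available here, the AEs/SAEs row of Table 2 seems to carry a mark under Screening. That row is damaged by extraction, and footnote t states the first dose, so the mark is not evidence either way.

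**2. Which study procedures come before the first dose?**

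| Procedure | Source | Limit |
|---|---|---|
| Chest CT without contrast | Section 7.2.3, Table 2 | Radiograph may replace it at Screening |
| Arterial blood gas | Section 7.2.1, Table 2 (Screening and Day 1) | Patients on invasive or non-invasive ventilation only |
| Laboratory blood draws | Section 8.8, Table 2 | Day 1 chemistry and hematology not repeated if done in the prior 24 hours |
| Baseline biomarker sample | Section 7.1.4 | Pre-dose on Day 1 |
| Pre-dose PK sample | Section 7.1.5 | Sampling moves to Day 2 if randomized in the afternoon |

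**3. What happens to a procedure-related SAE, by timing?**

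| Timing | Handling |
|---|---|
| Consent to first dose | Medical history; no SAE report required |
| First dose to Day 60 | SAE report within 24 hours (Section 8.3) |
| After the window | Report required; no deadline stated in that sentence (Section 8.3) |

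**4. Does the worsening rule close the gap?** In part. It captures a later change in a dosed patient. It does not produce a prompt report of the event itself. It yields nothing if the event resolves, stays stable or is fatal before dosing, or if the patient is never dosed.

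**5. Death after randomization, before dosing.** The patient is in the ITT Population and cannot meet the primary endpoint, which requires being alive at Day 28 (Section 7.1.1). Survival is also a key secondary endpoint at Days 28 and 60 (Section 7.1.2). The patient is not in the Safety Population, and the event precedes the SAE window. The duty to record fatal COVID-19 progression as an SAE applies within the safety reporting period, so it does not reach this case.

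**6. How long is the gap?** Table 2 places Screening on Day -1 to 1, and dosing follows randomization on Day 1. The interval therefore runs from hours to about 1-2 days.

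**7. How many events?** The documents give no rate. Assume, for illustration only, that 0 to 1% of patients are affected. With planned enrollment of 99 + 304 = 403, that is 0 to 0.01 × 403 ≈ 4 events. At the Phase 3 maximum, 99 + 608 = 707 gives 0 to about 7. Both ranges include zero.

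**The case against.** The strongest reply is that this is a deliberate and consistent convention. The AE definition in Section 8.1 concerns patients given a pharmaceutical product, and the SAE definition in Section 8.2 builds on it, so starting at first dose follows. Most pre-dose procedures are blood draws and imaging without contrast, recent results can often be reused, and the interval may be only hours. This stands, and it keeps the point small. It does not explain why Section 8.3 asks for procedure-related SAEs after the window but not before it.

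A reader might infer several stronger claims that the documents do not support:

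- **That the event is never recorded.** It goes into medical history, which is reviewed again on Day 1 before randomization (Table 2, footnote d), and later worsening in a dosed patient is reported as an AE.
- **That nothing reaches the IRBs or the iDMC.** The iDMC Charter and the detailed SAP to which the protocol defers are not in the text reviewed, and they could specify further listings. Section 11.4 also binds investigators to ICH GCP and applicable regulations.
- **That deaths before dosing are lost.** They enter the ITT efficacy data. The iDMC evaluates unblinded safety and efficacy data in Phase 2 (Section 9.2.4) and considers all available efficacy and safety data at the Phase 3 interim (Section 9.2.3).
- **That Sections 8.1.4 and 8.2 make all procedure harm reportable.** Their wording only limits the exemptions for disease progression and expected ARDS events. The asymmetry rests on Section 8.3 alone.

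**Conclusion.** The gap is real but narrow. By explicit and repeated rule, an SAE caused by a study procedure between consent and first dose is filed as medical history with no required 24-hour report, while Section 8.3 requires procedure-related SAEs to be reported after its window closes. Deaths and SAEs between randomization and first dose fall outside the SAE window; patients who are never dosed also fall outside the Safety Population, although their deaths count for efficacy.

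The size is small and cannot be estimated from the documents. The illustrative 0 to 4 events (0 to 7 at maximum enrollment) depend wholly on an assumed rate and should not be read as a forecast. The case rests on the wording of the reporting rule, not on frequency. No endpoint, sample size or test is affected. This is a cheap improvement to safety reporting, not a defect that threatens the trial's conclusions.

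**What to change.** 1. In the synopsis, Sections 8.1 and 8.3, and footnotes t and q of Appendix A, state that from signed consent to first dose any SAE the Investigator considers related to a study procedure is recorded and reported within 24 hours. All other pre-dose events remain medical history.
2. State that this applies to patients who are never dosed, since the present AE definition presupposes administration of a product.
3. Provide a listing, separate from the Safety Population outputs, of deaths and SAEs between randomization and first dose.
4. Check that the AEs/SAEs row of Table 2 agrees with its footnote and with the amended text.

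The cost is a short clause repeated in five places, a few additional SAE reports and one extra listing. Routine pre-dose events in critically ill patients would not become reportable, because the clause covers only serious events attributed to a study procedure.
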